
Recruitment and screening procedures are detailed in section 4.b and 4.d of this document, respectively. Informed consent for the study will take place using the following procedures. If a person fully meets eligibility criteria as determined through screening and continues to express interest in enrollment following screening, an informed consent session will take place either immediately or will be scheduled for a future time, depending on the individual's preference/availability. The consent process will take place either remotely through digital consenting available from REDCap or in person. In all cases, informed consent will be obtained only by authorized, trained study personnel affiliated with USC and not by employees of *Activ Sitting, Inc.* to avoid conflict of interest. Each prospective participant will be given time to read the consent and discuss their options with project staff and family members. To ensure ample time to peruse the consent information, we routinely mail or e-mail copies of a sample informed consent document to each interested party. When the prospective participant is ready, a dialogue regarding the study will ensue. The study team member is responsible for guiding the discussion, and will be instructed to follow a standard format to ensure all required elements are introduced. Explanations will cover all aspects of participation requirements, participants' rights, and other relevant information. Individuals will have an opportunity to ask questions about the study and, if they choose to enroll, will sign a consent form. They will be provided with a copy of the consent form.

Study Procedures: General

This study includes three stages: (1) Focus Group, (2) In-lab Testing, (3) In-home Testing. Study procedures for only the in-home testing phase are delineated below for purposes of clinicaltrials.gov.

Study Procedures: In-home Testing Stage

Overview. A separate set of users ($N=15$) who did not participate in the in-lab activities will complete an in-home trial of a *FitSitt* prototype. The trial period will last between 3 and 7 days (depending on availability of prototypes and scheduling) and will capture free-living feasibility, acceptability, and potential health-relevant short-term benefits of the system. Participation will require two in-person contacts within approximately a 2-week period, which will include pre-session activities, an in-home orientation to *FitSitt*, and a follow-up visit in-home.

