Pre-session activities. Participants will be mailed an activPAL and/or ActiGraph activity monitor package (including instructions and supplies) to do 3 days in advance of their initial in-home session. They will continue to wear these monitors for the duration of the chair trial period. This wear schedule will capture objective physical activity patterns prior to *FitSitt* availability, as well as activity patterns when the system is present in their home. Participants will also be sent electronic questionnaires (or hard copy if requested) to complete prior to their appointment. The battery of questionnaires (see Table 3) to be used at baseline include the same forms utilized in the in-lab session as well as an additional activity monitoring log [document "Activity Monitor Instructions Log" in iStar 21.2]. Any questionnaires left incomplete will be completed at the beginning of the in-home session.

In-home orientation. Participants will be provided with an in-home orientation to *FitSitt*. This session will be led by research personnel unaffiliated with *Activ Sitting, Inc.* Representatives of *Activ Sitting, Inc.* authorized to interact with participants may be present to help with device set-up and

installation as needed. The session will last approximately 2 hours. Personnel will use a checklist and data collection sheet to guide the visit and document necessary information [document “Tester Checklist Collect Home bsl” in iStar 21.2]. Included in this data collection form are a few open-ended questions as a mini-interview at baseline. This interview segment will be audio-recorded. The visit will generally address the following:

Daily activity engagement and environment: To aid in system placement, the research assistant will question users about their common daily activities and where they spend the most time sitting. (Responses will be documented.) Staff will recommend positioning the chair near this location, although users will make the final decision. The assistant will conduct a brief environmental scan to ensure the final location is safe and practical for the chair to be arranged. Final location details will be documented.

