Safety considerations and device care: The research assistant will discuss safety considerations. Participants will be shown how to enter and exit the chair safely. If used in free-standing applications (e.g., TV watching in the living room) where the foot extension and/or tray may be in the line of travel, as opposed to stowed in front of a desk/table, the research assistant will educate the user about safe maneuvering around the system. Research staff will also discuss safety concerning any power cords attached to the system and secure cords (if necessary) in a safe manner (e.g., taping to floor). The prototype currently has a design for breakaway magnetic cords such that if the system is plugged in at that time and a cord is tripped on, the cord releases the magnet to reduce the tripping hazard. Device care, such as avoidance of having liquids placed/used near the electronic components of the system will be discussed.

Activity and sensor monitoring: Users will be asked to continue wearing the activity monitors they had donned prior to the home session throughout the duration of the *FitSitt* trial period. They will be given additional supplies in the event either monitor falls off prior to completion of the prototype trial period. Users will be provided with an activity monitor log [document “Activity Monitor Instructions Log” in iStar 21.2] to keep track of wear periods. Users will also be informed that the *FitSitt* has embedded sensors that track system usage (e.g., treadle movements, seat occupancy) in real time and may provide reminders (e.g., vibration from the seat surface) if the user has sat for too long based on a movement goal set during fitting. At this time, they will also be given the Biostrap EVO to wear on either wrist for the entirety of the in-home trial period. This monitor will not be provided in advance like in the case of the activPAL and ActiGraph activity monitors. Therefore, the wear period will only be up to 7 days instead of 10 days as with the activPAL/ActiGraph. Participants will be instructed to avoid baths, swimming, and saunas to protect all activity monitors.

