Activity monitoring and physiological health data captured using ActivPAL, ActiGraph, and/or Biostrap, will be downloaded and cleaned upon return to the USC lab. Date-time stamps from the ActivPAL data, Biostrap data, ActiGraph data, and the *FitSitt* sensor data will allow correlation of activity and energy expenditure-related measures collected by the three systems. Questionnaires will be administered directly through REDCap database management system. REDCap is a secure, web-based application designed to support data capture for research studies, providing an intuitive interface for validated data entry. It also includes audit trails for tracking data manipulation and export procedures, automated export procedures for seamless data downloads to common statistical packages, and procedures for importing data from external sources. The REDCap website is password-protected and restricted to authorized users. All audio/video recordings will be transferred from the respective device from which they were recorded onto a password-protected, secure shared drive through the USC Chan Division; folders storing such data can only be accessed by authorized users. Any data collected in hard copy version that is not transferred to REDCap for electronic storage will be scanned in digital format to be stored on the aforementioned shared drive. The hard copies will be retained in a locked file cabinet in the USC Chan Division.

To minimize missing data, we will: (a) obtain alternate contact information for each participant at study entry; (b) employ one-on-one data collection when appropriate; (c) continuously monitor sensor output from *FitSitt* during in-home (remotely) and in-lab testing, (d) reschedule any missed data collection sessions, and (e) testers will receive regular refresher trainings across the study assessment periods to ensure they are adhering to all data collection guidelines. All study participants, including dropouts, will be described in terms of baseline characteristics. Reasons for missing data (e.g., activity monitor failure, participant hospitalization, participant withdrawal) will be documented to the extent possible.

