The various study stages will also include collection of a background/demographic profile comprised of factors such as *age, sex, race, ethnicity, other demographic characteristics, health-tracking habits, and household income*, and *access to in-home Wi-Fi*. Activity profile data will also be collected using self-report questionnaires addressing *physical activity level* and *self-efficacy to use FitSitt*. Activity and health monitor data (for in-lab and in-home stages) for assessment purposes will come from the research-grade activity monitor (ActivPAL and/or ActiGraph). Health and well-being indices include factors such as *ongoing health problems, health status, BMI (height and weight), pain severity, pain interference, fatigue, and stiffness*. Markers of acceptability of FitSitt are comprised of factors such as *initial impressions of FitSitt*, and address issues such as perceived engagement, and functionality. FitSitt usage data (for in-lab and in-home stages) will be obtained primarily from embedded sensors in the *FitSitt* system. Descriptive statistical analysis on all these variables will be generated for each sample and within key strata such as sex and age group (65–84, 85+) to characterize

the samples.

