In-home testing data related to activity, physiological parameters, and *FitSitt* usage patterns will only include activity that takes place during waking hours, as determined by ActivPAL's (and/or ActiGraph's) proprietary algorithm and corroborated by participant activity monitor logs. We will capture and report descriptive statistics on factors such as: *sitting/lying behavior* (total duration sitting/lying per day, mean duration of individual sitting/lying bouts over the day, number of sitting/lying bouts per day, number of sit-to-stand transitions per day), and *activity level* (total sedentary time [ActivPAL/ActiGraph proprietary algorithm], total step counts per day, total stepping time per day). Objective *FitSitt* usage data will be aggregated to produce meaningful summaries of chair usage, such as: *seat occupancy* (total duration sitting in *FitSitt* per day, duration of *FitSitt* sitting bouts per day), *treadle usage* (duration of pedaling bouts per day, frequency of pedaling bouts per day, total time pedaling per day, mean speed during daily pedaling bouts), *synchro-tilt/recline usage* (number of times recliner is engaged per day, mean duration of recliner engagement per day). Additionally, *pain, fatigue, stiffness, and physical activity/sedentary activity behaviors* (self-reported and objective) will be collected both pre-use of the system and at the conclusion of the study. Pre-post scores will be compared, for exploratory purposes, using a paired samples *t*-test (or Wilcoxon signed-rank test) to indicate changes, if any, after having *FitSitt* in the home for a short time. Additionally, we will explore the association of *FitSitt* adherence (minutes of treadle usage dichotomized at the median) to confidence to use *FitSitt* using Spearman correlation. Normalizing transformations will be applied to variables as appropriate; sparse data may be recoded to dichotomous or ordinal data.

Power Analysis

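### Does the Biostrap EVO need to be worn before the chair arrives, as the activPAL and ActiGraph are?

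*Combined protocol and SAP*

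**What the plan says.** Section 5.a.i treats the wearable devices differently. Under the pre-session heading, the activPAL and/or ActiGraph are mailed so that they can be worn for 3 days before the first home visit, and wear then continues through the chair period. The reason is given: "This wear schedule will capture objective physical activity patterns prior to" the chair's arrival, and then with the chair in the home. Under the heading on activity and sensor monitoring, the Biostrap EVO is given out at the orientation visit. The text says "This monitor will not be provided in advance like in the case of the activPAL and ActiGraph activity monitors", and adds that its maximum wear is therefore 7 days where the other two have 10.

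The overview in section 5.a.i says that the in-home stage is meant to capture, besides feasibility and acceptability, "potential health-relevant short-term benefits of the system". Section 5.a.v says "Activity monitoring and physiological health data captured using ActivPAL, ActiGraph, and/or Biostrap, will be downloaded and cleaned" when the devices come back, and that time stamps from the wearables and the chair sensors "will allow correlation of activity and energy expenditure-related measures collected by the three systems".

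Section 5.c begins one paragraph with "In-home testing data related to activity, physiological parameters, and" chair usage, and restricts these data to waking hours. The same paragraph lists the variables that "will be collected both pre-use of the system and at the conclusion of the study": pain, fatigue, stiffness, and self-reported and objective physical and sedentary activity. These are compared with a paired t-test or Wilcoxon signed-rank test, for exploratory purposes. Physiological parameters are not on that list. Earlier in section 5.c, monitor data used for assessment "will come from the research-grade activity monitor (ActivPAL and/or ActiGraph"). The Biostrap appears neither in Table 3 nor in section 5.b.iii.

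**The concern.** The in-home stage has one group, so a participant's own days before the chair are the only possible comparator from before FitSitt. The protocol accepts this reasoning for the activPAL and ActiGraph and does not apply it to the Biostrap, nor does it say why. Physiological parameters are named among the in-home data, and the Biostrap looks like a natural source for them. If the short-term benefits in the overview were meant to include change in those parameters, the schedule could not show it. A trend within 3 to 7 chair days is not a change from before the chair, and no later analysis can recover days that were never recorded.

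At stake would be a reader taking Biostrap results as evidence of early benefit, and carrying that into the Phase II planning that the Power Analysis section says this pilot will inform.

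**Working it through.** **Wear days per participant.** Inputs: 3 pre-visit days (section 5.a.i, pre-session activities), 3 to 7 chair days (section 5.a.i, overview), no early issue of the Biostrap (section 5.a.i, activity and sensor monitoring).

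| Device | Before chair | With chair | Total |
|---|---|---|---|
| activPAL/ActiGraph | 3 | 3 to 7 | 6 to 10 |
| Biostrap, as written | 0 | 3 to 7 | 3 to 7 |
| Biostrap, if mailed early | 3 | 3 to 7 | 6 to 10 |

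The maxima of 10 and 7 reproduce the protocol's own figures. Their difference, 10 − 7 = 3 days, is exactly the missing baseline. The timing fact is therefore right: 0 of 15 participants can give a pre-chair contrast on this device as written, and up to 15 of 15 could with early wear.

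**Which planned analyses need those 3 days?**

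| Planned use | Needs pre-chair Biostrap data? |
|---|---|
| Pre-post test of pain, stiffness, fatigue (5.c; questionnaires pre and post in Table 3) | No |
| Pre-post test of self-reported activity (5.c; PASE pre and post in Table 3) | No |
| Pre-post test of objective activity (5.c; activPAL/ActiGraph) | No, these have 3 days |
| Time-stamped correlation across devices and chair sensors (5.a.v) | No, concurrent wear is enough |
| Physiological parameters in waking hours (5.c) | No pre-post test named, no variable named |

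No planned comparison is lost.

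**What early wear would buy.** The half-width of a 95% confidence interval for a mean paired change, in standard deviations of the differences, is t(0.975, n − 1)/√n.

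- n = 15 (everyone complete): 2.145/3.873 = 0.55
- n = 12 (assumed): 2.201/3.464 = 0.64
- n = 10 (assumed): 2.262/3.162 = 0.72

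This is rough exploratory precision, for a variable that the plan does not name.

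**What early wear would cost.** Biostrap wear as written is 15 × 3 = 45 to 15 × 7 = 105 participant-days. With early mailing it is 15 × 6 = 90 to 15 × 10 = 150, an increase of 15 × 3 = 45. The document gives no unit count, set-up needs or turnaround time for the device, so the practical cost cannot be worked out. The total would stay within the 10 days of monitor wear that Table 2 compensates, though that line does not show that 10 days on the Biostrap was intended.

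**The case for a change.** The best argument for a change is that stating a wear schedule is not the same as stating what it means for inference. Nowhere does the protocol say that Biostrap data are descriptive or usage-linked only. Section 5.a.v puts the Biostrap together with the other two devices as a source of physiological health data, while section 5.c names only the activPAL and/or ActiGraph for assessment. A monitor package already goes out 3 days ahead, so adding a wrist device may look cheap, and lost baseline days cannot be made up later.

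Part of this stands. The device's role is under-described: it is missing from Table 3 and section 5.b.iii, and no physiological variable is named. These are documentation gaps, and they are separate from when the device is worn.

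The rest carries less weight. That the Biostrap is the main physiological source is an inference, since section 5.a.v names three devices jointly and no text shown says what the Biostrap measures. The overview's phrase on benefits names no device, and the questionnaires and activity measures can serve it in full. The omissions from Table 3, section 5.b.iii and the assessment sentence fit a supplementary device better than an outcome instrument that lacks its baseline. Parts of the system description in section 5.a.ii are redacted, so the device's role may be explained there, and that cannot be held against the plan. Finally, the orientation visit also delivers education on sedentary behaviour and movement goals, so even a complete before-and-after contrast on the Biostrap could not isolate the chair.

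**Conclusion.** The observation is correct but does not call for a change. The Biostrap has 0 pre-chair days by an openly stated choice, and its data cannot show change from before FitSitt. Followed as written, the plan still gives no wrong result: every variable on the pre-post list has its baseline from another source, and the stated use of Biostrap data needs only concurrent wear.

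The aim of this stage is feasibility, acceptability and safety; the pre-post tests are exploratory, and efficacy is left to a larger study. Earlier wear is a choice the sponsor could reasonably make or leave. It would add a comparison with a half-width of 0.55 to 0.72 standard deviations of the differences, for 45 extra participant-days and unknown supply and set-up costs. The gaps in Table 3, section 5.b.iii and the naming of parameters are ones that analysts would fill sensibly, by describing Biostrap measures over the trial period or relating them to chair use and claiming no change from baseline.

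This rests on two assumptions: that the pre-post list in section 5.c is complete as written, and that the short-term benefits in the overview refer to the variables on that list. If the sponsor did intend a physiological before-and-after claim from the Biostrap, the schedule could not support it.

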Use expectations: The assistant will explain expectations for use of the chair during the study period. *FitSitt* will be presented as a tool useful for breaking up sitting without impeding desired activities—focus is not on its exerciser function but rather its capacity to reduce sedentary activity. Because we hypothesize that benefits will accrue at even low resistance settings, the assistant will encourage individuals to use the chair for brief, light activity with low resistance (as preset during fitting). The resistance setting follows empirical evidence supporting replacement of sedentary activity with light physical activity (Buman et al., 2010). Two types of evidence-based recommendations for treadle use will be offered to the user for which they can choose their most preferred: (1) when occupying the chair, pedal at their leisure across the day, with a goal of

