interrupting 30-minute sitting periods with microbursts (1–3 minutes) of treadle use. Although no unified guidelines exist yet for reducing sedentary activity (Ryan et al., 2011), this dose is based on recommendations for persons with low-back pain (Atlas & Deyo, 2001) and is linked to reduced fatigue (Bergouignan et al., 2016), increased energy (Bergouignan et al., 2016), improved mood (Wennberg et al., 2016), and good metabolic health (Owen et al., 2010); or (2) pedal at their leisure across the day, with a goal of interrupting each hour of sitting with at least 5 minutes total of light movement. This second break length was informed by a Bond's study whereby disrupting each hour with a six-minute break was preferred over 3-minute breaks every 30 minutes and 12-minute breaks every 120 minutes in adults with overweight/obesity (Bond et al., 2014). Participants will also be encouraged to use the system as their primary seat, especially in instances where extended sitting is common such as while one works at a table/desk or during TV viewing. The assistant will further explain that although the more one accesses the treadle portion, the greater the energy expenditure, there is no expectation for continued use throughout the day; rather one should use the device at leisure and when comfortable and convenient to break up sedentary time. Participants will also be instructed to avoid using the treadles for more than one hour in total throughout the day to minimize any acute soreness potentially felt secondary to increased activity. Other features that promote movement such as the synchro-tilt recline to stretch the body and/or the rocking condition to engage core muscles will also be encouraged to use.

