Follow-up activities and equipment removal. After trialing the chair for 3 to 7 days, a follow-up visit will take place, which can occur in-person, virtually, or in hybrid format. (*FitSitt* equipment retrieval must be in person.) Self-report questionnaires (see Table 3) will be emailed in advance of the visit for completion. An audio-recorded semi-structured interview (see section 5.b.ii) to discuss the users’ experiences during the study will be completed either virtually or in-person [document “Follow-up In-home Interview Guide” in iStar 21.2]. Research or Activ Sitting, Inc. staff will arrange to remove the chair and collect any other equipment (e.g., activity monitor) upon completion of follow-up activities.

Compensation

Participants will be compensated for their time to complete individual activities for the various stages of studies. Payment will be given by check mailed at the end of study participation and will be prorated based on activities they complete. The payment schedule for the in-home stage is delineated below in Table 2.

Table 2: Schedule of compensation/costs for each study stage

In-home Testing Stage (up to \$165 total at end of study)

 • \$10 complete questionnaires at the beginning of the study • \$20 wear an activity and health monitor for up to 10 days • \$40 complete a 2-hour in-home orientation to FitSitt • \$50 utilize a FitSitt prototype in home for 3 to 7 days • \$10 complete questionnaires at the end of the study • \$20 complete a follow-up interview • \$15 return the loaned activity and health monitors

5.a.ii. Intervention details: *FitSitt* system

The *FitSitt* is a specialized wellness seating system [document “FitSitt Brochure” in iStar 40.1] to reduce and reverse negative outcomes of inactivity in older adults. The core chair provides seat-based stepping movement, full-body postural support that responds to and facilitates stepping actions, and reclining capabilities to allow stretching/postural changes, all of which are intended to be seamlessly integrated into individuals’ daily routines and living spaces. The system will be enhanced using stakeholder feedback along the stages of development, adding specialized older adult-custom features that are tailored to older adults’ expressed needs. To-date, no other fitness platform tailored to older consumers has been systematically developed and optimized to address sedentary activity in the aging population.

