MPI [name] will oversee general data management and analytic functions with guidance from the USC team’s statistician. [name]’s team will collaborate with authorized *Activ Sitting, Inc.* and *Senseer Health Inc.* personnel regarding data management of sensor-captured data from *FitSitt* or any wearables linked to the system. *Activ Sitting* and *Senseer Health Inc.* will store, clean, and transfer raw usage data obtained from *FitSitt* sensors through secure cloud-based services (Linode Cloud Computing Platform [allowing HIPAA compliant storage and transfer] and SharePoint [protected through USC]). These data will be transferred to MPI [name]’s team after initial formatting for secure storage on USC’s protected network and shared drive.

To reduce the amount of artificial data captured from *FitSitt* during in-home trials, participants will be asked to reframe from allowing anyone else to use the system and to discourage animals from

sitting on the device. Additionally, participants will be queried during the follow-up interviews at home-based sessions about any instances that may have caused artificial usage readings.

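### The exploratory pre-post activity outcomes do not separate seated treadling, which occurs only after the chair arrives, and leave the source monitor open

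*Combined protocol and SAP*

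**What the plan says.** The in-home outcomes are in section 5.c. They fall into a posture group (daily sitting or lying time, bout length, bout number, sit-to-stand transitions) and an activity group: "total sedentary time [ActivPAL/ActiGraph proprietary algorithm], total step counts per day, total stepping time per day". Self-reported and objective activity and sedentary behaviors are taken before use and at the end. They are compared, as exploration, by a paired t-test or Wilcoxon signed-rank test. Pedaling time and bouts from the chair's sensors are listed separately as usage summaries.

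On the intervention, section 5.a.ii states: "The core chair provides seat-based stepping movement". Under Use expectations in 5.a.i, the rationale for low resistance is this: "The resistance setting follows empirical evidence supporting replacement of sedentary activity with light physical activity". One of the two goals offered is "interrupting each hour of sitting with at least 5 minutes total of light movement". The other is a burst of 1–3 minutes of treadling per 30 minutes of sitting. Participants are also told to "avoid using the treadles for more than one hour in total throughout the day".

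On the monitors, 5.b.iii puts the activPAL on the thigh, for seated and standing activity. It puts the ActiGraph on the ankle or shoe, because that site is expected to register the treadle motion. Pre-session activities (5.a.i) and 5.c both use and/or wording for the two devices. Section 5.a.v says that the date-time stamps of the monitors and chair sensors "will allow correlation of activity and energy expenditure-related measures collected by the three systems".

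**The concern.** A pre-post comparison of whole-day totals assumes that the measure means the same thing in both periods. Here one behavior, seated treadling, cannot occur at baseline and is encouraged afterwards. However a monitor scores it, the effect falls wholly in the post period.

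Two readings of the same participant are then possible. If the ankle or shoe device counts strokes as steps, steps and stepping time can rise with no extra walking. If the thigh device scores the minutes as sitting, sedentary time can stay unchanged in someone who did what the chair asks. Which picture appears depends on a choice of device that the plan leaves open.

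The Power Analysis section says the study tests procedures for a larger study of decreasing sedentariness. What is at stake is the definition of the outcome carried forward, and how any change in this pilot is described.

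**Working it through.** The plan gives no effect size, SD, alpha or power for these outcomes, so there is no figure to reproduce. The check sets the text side by side and then gives a scale.

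**1. What is defined (section 5.c)**

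| Outcome | Source monitor named | How treadling enters |
|---|---|---|
| Sedentary time | Both, separated by a slash | Not stated |
| Steps, stepping time | None | Not stated |
| Sitting-bout number and mean length | None | Not stated |
| Sitting or lying time | None | None needed: a person treadling is still seated |

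**2. Treadle minutes implied by the stated goals**

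- Goal 1: 1–3 min per 30 min of sitting = 2 × (1 to 3) = 2–6 min per hour.
- Goal 2: at least 5 min per hour, if met by pedaling.
- Assuming 4 to 8 hours a day in the chair (not in the documents): goal 1 gives 4 × 2 = 8 up to 8 × 6 = 48 min/day; goal 2 gives at least 4 × 5 = 20 to 8 × 5 = 40 min/day.
- Advised maximum: 60 min/day. This is an instruction, not an enforced bound.

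**3. Effect of scoring alone**

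Let T be treadle minutes per day, with all other behavior unchanged. Let q be the share of them that the monitor scores as sedentary, and s the share scored as stepping. Both are unknown, from 0 to 1.

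- Apparent change in sedentary time = −(1 − q)T. At T = 30 this is 0, −15 or −30 min/day for q = 1, 0.5 or 0. At T = 60 it is 0, −30 or −60.
- Apparent change in stepping time = +sT, so 0 to +60 min/day at T = 60.
- Change in stepping time outside treadle bouts = 0 at every s, because treadled minutes are removed however they were scored.
- Sedentary time with time-matched treadle minutes counted as non-sedentary: −(1 − q)T − qT = −T at every q. This no longer depends on the device, but it simply restates treadle time.

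**4. Bout measures**

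Take a 2-hour sit with 3-minute bursts at three break points. If treadling counts as sitting, it is one bout of 120 min. If treadling counts as a break, it is four bouts averaging (120 − 9)/4 = 27.75 min.

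**5. Could a scoring shift look like a finding?**

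This uses a two-sided paired t-test with n = 15, alpha 0.05 and noncentrality (shift/SD) × √15. Alpha and the SD of the paired change are assumptions.

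| Shift from scoring alone | SD 60 | SD 90 | SD 120 min/day |
|---|---|---|---|
| 30 min/day | 0.438 | 0.225 | 0.147 |
| 60 min/day | 0.949 | 0.671 | 0.438 |

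These are probabilities of p < 0.05 if that shift occurred. They do not show that it would.

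**6. Who wears what**

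Table 3 lists both devices as worn throughout. The monitoring paragraph in 5.a.i supplies spares "in the event either monitor falls off prior to completion of the prototype trial period", which suggests two devices per person. Pre-session activities says one and/or the other is mailed. The documents do not settle it.

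**The case against.** The best defense is that the plan already holds most of what is needed. Section 5.c separates posture from activity level, and posture needs no treadling rule. Section 5.b.iii points to the activPAL for sitting. For sedentary time the named algorithm's default scoring is itself a rule. Treadle data are collected and time-stamped, so scoring can be examined later. Section 5.b.iii also foresees comparing the activPAL with chair sensors and video, and the in-lab stage, left out of this version, may show how treadling is scored. The outcome list is illustrative, the comparison exploratory, and no decision hangs on it.

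Much of this stands. Sitting or lying time is well defined as posture, and the stakes are low. But two algorithms are named for sedentary time, no outcome is assigned to a device, and the ability to link data is not a rule for using the link. Pedaling time is reported beside the pre-post outcomes and never enters them.

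A reader might infer more: that the plan will overstate steps or a fall in sedentary time, or that the sample is split between devices. The documents support neither. They do not describe how either algorithm scores treadling, and the wear wording is compatible with everyone wearing both.

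**Conclusion.** The point holds and is minor. Total sedentary time, steps, stepping time and the sitting-bout measures are compared across two periods, of which only the second can contain treadling, with no separation and no fixed source monitor. Among participants who follow the advised limit, up to about 60 min/day could be scored either way. The values at 30 min/day and the test probabilities rest on assumed treadle time, scoring shares and SDs.

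Neither direction nor size of bias can be established from these documents. The comparison is exploratory in 15 people, so no confirmatory claim is at risk. The effect is on how a change, or its absence, is read and on the outcome definition passed to the larger study. This is still more than missing detail: comparing steps and stepping time outside treadle bouts with baseline is better than comparing whole-day totals, and the planned data allow it.

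**What to change.** In section 5.c:

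1. For each pre-post objective outcome, name one source monitor, the same in both periods. Do not pool participants measured by different monitors.
2. Use the time stamps described in 5.a.v and the chair's treadle bouts to split post-period steps and stepping time into inside and outside bouts. Compare the outside part with baseline, report the inside part separately, and keep the unadjusted totals.
3. Report total sedentary time, sitting-bout number and mean bout length twice: as scored by the monitor, and with time-matched treadle minutes counted as non-sedentary. State that the second version of sedentary time falls mechanically with treadle use and is not evidence of efficacy. Leave sitting or lying time as a posture measure.

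Before the merge, remove chair readings flagged in the follow-up interview, which already asks "about any instances that may have caused artificial usage readings".

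The cost is analysis wording and a merge of data already planned. If some participants wear only one monitor, outcomes assigned to the other will have fewer than 15 people. The split needs clean chair-sensor data and aligned clocks: a 1-minute offset misplaces 1/3 of a 3-minute burst and all of a 1-minute burst, so alignment must be checked first.
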